4.3.8.2. Peripheral Blood Blasts

Peripheral blood blasts will be summarized over time for all patients.

The number and percentage of patients with $\geq 50\%$ reduction in peripheral blood blasts from baseline and the number and percentage of patients with 0 % blasts will be summarized at any time for CMML patients with baseline blasts $\geq 0\%$.

The maximum percent reduction from baseline and the maximum increase from baseline across all post-baseline visits will be summarized for CMML patients. A waterfall plot of the maximum percent reduction in blasts, blasts at Cycle 4 Day 21 visit, and blasts at Cycle 7 Day 28 will be created.

Mean and standard error will be plotted over time for CMML.

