10. Patient has 2016 WHO-defined CMML-1 (2-4% blasts in peripheral blood and/or 5-9% blasts in bone marrow) and CMML-2 (5-19% blasts in peripheral blood and/or 10-19% blasts in bone marrow, and/or presence of Auer rods) (Arber 2016).
11. Patient is refractory/resistant/intolerant, as defined for the purposes of this study (in the absence of a standard definition for CMML) below, to HMAs, or HU, or intensive chemotherapy, including:
 - **Resistance/intolerance to HU** is defined as:
 - Uncontrolled myeloproliferation, (platelets $> 400 \times 10^9/L$ and WBC $> 10 \times 10^9/L$ after 3 months of at least 2 g/day of HU); **or**
 - Myelosuppression at a clinically relevant dose; **or**
 - Presence of unacceptable HU-related non-hematological toxicities, such as mucocutaneous manifestations, gastrointestinal symptoms, pneumonitis or fever at any dose of HU.

Conventional definition for HMA failure is defined for the purposes of this study (in the absence of a standard definition for CMML) as:

- Disease progression following at least 4 to 6 cycles of 5-azacitidine or decitabine; or
- Relapse after achieving response; or
- Intolerance to 5-azacitidine or decitabine at the prescribed dose.

OR

Patient is classified as high-risk based on the presence of morphological features, as described by the 2016 WHO prognostic system (Arber 2016), and the clinical and molecular features described in molecularly-integrated prognostic systems, such as the Groupe Français des Myélodysplasies (GFM), Mayo Molecular Model (MMM), and the CMML specific prognostic model (CPSS-Mol) (Woo 2020) and thus is not expected to benefit from HMAs.

12. Patient is ineligible for an immediate allo-SCT.

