3.2. General Methods

All data listings that contain an evaluation date will contain a relative study day (Rel Day). Pre-treatment and on-treatment study days are numbered relative to the day of the first dose of study medication which is designated as Rel Day 1. The preceding day is Rel Day -1, the day before that is Rel Day -2, etc. The last day of study medication is designated with an "L" (e.g., Rel Day 14L). Post-treatment study days are numbered relative to the last dose and are designated as Rel Day 1P, Rel Day 2P, etc.

All output will be incorporated into Microsoft Rich Text File or Excel files, or Adobe Acrobat PDF files, sorted and labeled according to the International Conference on Harmonisation (ICH) recommendations, and formatted to the appropriate page size(s).

Tabulations will be produced for appropriate demographic, baseline, efficacy, safety, and immunogenicity parameters. For categorical variables, summary tabulations of the number and percentage of patients within each category (with a category for missing data) of the parameter will be presented. Two-sided 95% confidence intervals (CIs) will be computed using the Clopper Exact method. For continuous variables, the number of patients, mean, median, standard deviation, minimum, and maximum values will be presented. Time-to-event data will be summarized using Kaplan-Meier methodology using 25th, 50th (median), and 75th percentiles with associated 2-sided 95% CIs, as well as percentage of censored observations.

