3.5. Methods of Pooling Data

Disposition, baseline, and safety summaries will be displayed by dose as well as by disease and trial stage. Tabulations presented by dose will include a summary of each dose level for MF and for CMML separately.

7 µg/kg/day	9 µg/kg/day	12 µg/kg/day	Overall
-------------	-------------	--------------	---------

Tabulations presented by disease and trial stage will include a summary of each stage for MF (Stages 1 and 2) and for CMML (Stages 1, 2, and 3A).

MF			CMML			
Stage 1 (N=xx)	Stage 2 (N=xx)	Overall (N=xx)	Stage 1 (N=xx)	Stage 2 (N=xx)	Stage 3A (N=xx)	Overall (N=xx)

For myelofibrosis patients, summaries will be displayed by Dynamic International Prognostic Scoring System (DIPSS)-Plus Risk for treatment naïve and for relapsed/refractory patients separately.

Intermediate-1	Intermediate-2	High	Overall
----------------	----------------	------	---------

For chronic myelomonocytic leukemia patients, summaries will be displayed by CMML Type for treatment naïve and for relapsed/refractory patients separately.

CMMI-1	CMMI-2	Overall
--------	--------	---------

One patient with SM was treated in Stage 2 and will be presented in data listings. No patients with PED were treated so no separate tabulations or listings will be presented.

Summaries of efficacy results will be displayed separately for MF and CMML patient groups treated at 12 µg/kg, and separately for patients treated at 7 or 9 µg/kg. Efficacy results for MF patients will be presented separately for treatment-naïve and relapsed/refractory patients. For myelofibrosis patients, summaries will be displayed by DIPSS-Plus Risk for treatment naïve and for relapsed/refractory patients separately. For chronic myelomonocytic leukemia patients, summaries will be displayed by CMML Type for treatment naïve and for relapsed/refractory patients separately.

Treatment Naïve (N=xx)	Relapsed/ Refractory (N=xx)	Overall (N=xx)
---------------------------	--------------------------------	-------------------

Efficacy summaries of investigator report response data for CMML patients will be presented separately for treatment-naïve and relapsed/refractory patients, with Stages 1 and 2 presented separately from Stage 3A patients.

Stages 1-2			Stage 3A		
Treatment	Relapsed/ Refractory	Overall	Treatment	Relapsed/ Refractory	Overall
Naïve (N=xx)	(N=xx)	(N=xx)	Naïve (N=xx)	(N=xx)	(N=xx)

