3.10. Missing, Unused, and Spurious Data

In general, there will be no substitutions made to accommodate missing data points. All data recorded on the eCRF will be included in data listings that will accompany the CSR.

For categorical variables, a category for missing data of the parameter will be presented. Percentages will be calculated from the total population, including patients with missing results.

When tabulating AE data, partial dates will be handled as follows. If the day of the month is missing, the onset day will be set to the first day of the month unless it is the same month and year as study treatment. In this case, in order to conservatively report the event as treatment-emergent, the onset date will be assumed to be the date of treatment. If the onset day and month are both missing, the day and month will be assumed to be January 1, unless the event occurred in the same year as the study treatment. In this case, the event onset will be coded to the day of

treatment in order to conservatively report the event as treatment-emergent. A missing onset date will be set up to the first day of treatment.

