4.2. Demographics and Baseline Characteristics

Demographics and baseline characteristics will be summarized as described in [Section 3.5](#). Age, height, and weight will be summarized using descriptive statistics (number of patients, mean, SD, median, minimum, and maximum). The number and percentage of patients in each gender, race, ethnicity, and ECOG PS categories also will be presented.

Primary disease history will be summarized for MF and CMML. MF disease history will include DIPSS-plus score risk factors and profile, type of MF (primary, post polycythemia, post essential thrombocythemia), type of abnormal karyotype, mutation status, and time since diagnosis. CMML disease history will include diagnosis criteria, CMML type (CMML-1 or CMML-2), symptoms, cytogenetic risk profile, monocytic cell nodules in bone marrow biopsy (yes/no), mutations, prognostic scoring system molecular risk profile, and time since diagnosis. Baseline laboratory data, including monocytes, platelets, hemoglobin, white blood cell, lactate dehydrogenase, bone marrow blasts, peripheral blood blasts, will be summarized for all patients. Additionally, baseline MPN-SAF TSS, transfusion dependence status (yes/no) for red blood cells and platelets, spleen size by MRI/CT and by Physical Exam, the presence of splenomegaly at baseline (yes/no), and the presence of hepatomegaly at baseline (yes/no) will be summarized for all patients. SM disease history will be included in a data listing and will include diagnosis criteria, mutations, and molecular markers..

Receipt (yes/no) of prior systemic therapy, prior radiation therapy, and prior stem cell transplant (SCT) will be summarized. The number and type of prior systemic therapy for MPN will be presented. The reason why the patient was not considered an immediate candidate for SCT will also be summarized.

All analyses of demographic/baseline data will be performed using the Safety Population and select analyses will be repeated using the mITT Population.

Demographic, baseline, medical history, and disease history data for each patient will be provided in data listings.

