4.3.8. Laboratory Efficacy Results

4.3.8.1. Bone Marrow Blasts

Bone marrow blasts will be summarized over time for all patients. In case of different methods used to assess bone marrow at the same visit (i.e aspirate and biopsy) but only one method was used at baseline, the method used at baseline will be considered for comparison. In case both methods are used in all visits, the larger blast results between biopsy results and aspirate results for a subject will be presented. In case only one method is used in a specific visit, it will be considered regardless the method used at baseline.

The number and percentage of patients with $\geq 50\%$ reduction in bone marrow blasts from baseline and the number and percentage of patients with $< 5\%$ blasts will be summarized at any time for CMML patients with baseline blasts $\geq 5\%$.

The maximum percent reduction from baseline and the maximum increase from baseline across all post-baseline visits will be summarized for CMML patients. A waterfall plot of the maximum percent reduction in blasts, blasts at Cycle 4 Day 21 visit, and blasts at Cycle 7 Day 28 will be created.

Mean and standard error will be plotted over time for CMML.

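### Two descriptive SAP rules are wrong as printed: the peripheral-blast rates do not exclude patients who start at 0%, and the PCS-High vital-sign column asks for a fall from baseline.

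*SAP*

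**What the plan says.** **Peripheral blasts.** SAP 4.3.8.2 gives two at-any-time rates for CMML patients: at least a 50% reduction from baseline, and 0% blasts. The restriction attached to them reads "patients with 0 % blasts will be summarized at any time for CMML patients with baseline blasts $\geq 0" percent. The parallel marrow section, SAP 4.3.8.1, has the same sentence form with a threshold that does exclude patients: "patients with $< 5\%$ blasts will be summarized at any time for CMML patients with baseline blasts $\geq 5" percent. Protocol 7.1.1, criterion 10, opens "Patient has 2016 WHO-defined CMML-1 (2-4% blasts in peripheral blood and/or 5-9% blasts in bone marrow"; the and/or lets marrow blasts alone qualify a patient, and the CMML-2 limb is built the same way.

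On missing data, SAP 3.2 asks for "summary tabulations of the number and percentage of patients within each category (with a category for missing data) of the parameter will be presented", and SAP 3.10 adds "Percentages will be calculated from the total population, including patients with missing results".

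**Vital signs.** The table in SAP 4.4.4 defines potentially clinically significant (PCS) values by an observed value and a change from baseline. The PCS-Low and PCS-High halves carry the same change heading, a decrease. The PCS-High limits are above 180 mmHg systolic with a change of at least 20 mmHg, above 105 mmHg diastolic with at least 10 mmHg, and above 120 bpm heart rate with a change of at least 15, printed in mmHg. The table does not say how the two conditions are joined.

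**The concern.** In SAP 4.3.8.2 the author added a baseline clause, but as printed it screens out only patients with no baseline value. The rate of 0% blasts then mixes patients who cleared blasts with patients who had none to clear, while the reduction rate has no defined value for the second group. SAP 1.2.5.1 lists blast results among the component data to be assessed as secondary endpoints, so a reader of the study report may take the 0% rate as a clearance rate.

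In SAP 4.4.4 a treatment-emergent high value defined through a fall makes no sense. What is at stake is the count of patients with upward shifts in blood pressure or heart rate in a safety table.

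**Working it through.** Neither rule carries a stated figure to reproduce, so each is applied as printed and as corrected.

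**(a) Peripheral blasts**

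Let s be the share of patients at 0% at baseline, a the share of those with a later 0% value, c the clearance rate among patients who start with blasts, and r the rate of at least 50% reduction among patients who start with blasts. None of these is in the documents.

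1. 0% rate as printed: s·a + (1 − s)·c.
2. 0% rate with baseline above 0%: c.
3. Difference: s·a + (1 − s)·c − c = s(a − c). It is positive when s > 0 and a > c. Since a single later 0% value is enough, a patient who starts at zero will usually meet the target, so a > c is the expected case.
4. If s = 0 the difference is 0.
5. Percent reduction from a baseline of 0 divides by zero, so such a patient cannot be a reducer. If the patient stays in the denominator, r is reported as (1 − s)·r.

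Arithmetic illustration only: with s = 1/3, a = 1 and c = 0.25, the difference is 1/3 × 0.75 = 0.25, so a clearance rate of 25% is reported as 50%. With r = 0.25, the reduction rate is reported as 2/3 × 0.25 = 16.7%. With s = 0 both rates are correct.

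The missing-data rules do not repair the 0% rate, because a later 0% is a valid result. They might expose the undefined reductions, but neither SAP 3.2 nor 3.10 says that a derived value with a zero baseline is classed as missing.

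**(b) PCS-High as printed**

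Under AND, a flag needs an observed value above the limit and a fall of at least the stated change:

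- Systolic: baseline above 180 + 20 = 200 mmHg.
- Diastolic: baseline above 105 + 10 = 115 mmHg.
- Heart rate: baseline above 120 + 15 = 135 bpm, reading the change in bpm.

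| Systolic course | Printed, AND | Printed, OR | Increase, AND | Increase, OR |
|---|---|---|---|---|
| 140 to 185 mmHg | not flagged | flagged | flagged | flagged |
| 140 to 115 mmHg | not flagged | flagged as high | not flagged | not flagged |

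Under AND the printed rule misses the rise. Under OR it catches the rise on its observed value but also labels a fall of 25 mmHg as high. Either way the count is wrong. With an increase heading both courses are classified sensibly under either connector.

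**The case against.** The strongest reply on (a) is that the SAP often reports attained status rather than conversion. Sections 4.3.8.3 to 4.3.8.6 count monocytes, white cells, hemoglobin and platelets within normal limits at any time, with no baseline clause, so patients normal at baseline count there too. That stands as a description of those sections, and it means 4.3.8.2 sits between two conventions. It does not rescue the printed rule: 4.3.8.2 does carry a baseline clause, like the marrow section, and the clause has almost no effect. Nor does it help the percent reduction, which is undefined at a zero baseline under either convention.

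A reader might infer a large inflation of the 0% rate. The documents do not support a size. Criterion 10 is the Stage 3A criterion and shows only that a 0% baseline is possible, not how common it is. Planned Stage 3A cohort sizes would not help: SAP 5 records that enrollment was not continued, and SAP 3.5 does not set those cohorts as the columns for this output.

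On (b), a reader might infer that a rise can never be flagged. That holds in general only under AND. The missing connector is a gap in detail, not an error in itself. It is also fair that the table's own title shows the intent and that a nearly empty PCS-High column under AND would probably be noticed.

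Finally, the listings, the baseline summary ("bone marrow blasts, peripheral blood blasts, will be summarized for all patients") and the actual-value and change summaries for vital signs allow a check, and the table shells, which SAP 9 places in a separate document, may already be right. If they are, they contradict the governing text, which still needs correcting.

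**Conclusion.** Both rules are wrong as printed, and no other section of either document corrects them.

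For (a), the 0% rate is biased upward by s(a − c) if any patients start at 0% and a exceeds c. Only the direction can be stated, because s is unknown and may be zero. For (b), the PCS-High count is wrong under either connector, though in different ways, and the heart-rate change has the wrong unit.

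A reader might go further and conclude that the efficacy result is inflated. It is not: ORR is investigator-assessed CR or PR and does not use this rate, and the sample-size reasoning does not depend on it. Both outputs are descriptive. Severity is minor.

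**What to change.** - **SAP 4.3.8.2:** replace the threshold of at least 0% with above 0% for both rates, and show the number of CMML patients with baseline peripheral blasts above 0% as the denominator, parallel to 4.3.8.1.
- **SAP 4.4.4:** head the PCS-High change column as an increase from baseline and give the heart-rate change in bpm. While the table is open, the sponsor can also state how the observed-value and change conditions are joined; the documents do not settle this.
- **Table shells:** check the separate shells against both edits, and confirm the sign and the column heading in the source SAP file.

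The cost is a few words in two sections and a check of the shells. The downside is a smaller denominator and a wider confidence interval for the blast rates if some patients do start at 0%. The loss is felt most in the split columns, since under SAP 3.5 "summaries will be displayed by CMML Type", separately for treatment-naive and relapsed/refractory patients.

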4.3.8.3. Absolute Monocyte Count

Absolute monocyte counts will be summarized over time for all CMML patients.

The number and percentage of patients with $\geq 50\%$ reduction in absolute monocyte count from baseline and the number and percentage of patients with counts within normal limits will be summarized at any time.

The maximum percent reduction from baseline and the maximum increase from baseline across all post-baseline visits will be summarized. A waterfall plot of the maximum percent reduction in counts, counts at Cycle 4 Day 21 visit, and counts at Cycle 7 Day 28 will be created.

Mean and standard error will be plotted over time for CMML.

4.3.8.4. White Blood Cell Count

White blood cell counts will be summarized over time for all patients.

The number and percentage of patients with $\geq 50\%$ reduction in white blood cell count from baseline and the number and percentage of patients with counts within normal limits will be summarized at any time for CMML patients.

The maximum percent reduction from baseline and the maximum increase from baseline across all post-baseline visits will be summarized for CMML patients. A waterfall plot of the maximum percent reduction in counts, counts at Cycle 4 Day 21 visit, and counts at Cycle 7 Day 28 will be created.

Mean and standard error will be plotted over time.

4.3.8.5. Hemoglobin

Hemoglobin will be summarized over time for all patients.

The number and percentage of patients with ≥ 20 g/L increase in hemoglobin from baseline and the number and percentage of patients with results within normal limits will be summarized at any time for CMML patients.

The maximum percent reduction from baseline and the maximum increase from baseline across all post-baseline visits will be summarized for CMML patients. A waterfall plot of the maximum increase in hemoglobin, hemoglobin at Cycle 4 Day 21 visit, and hemoglobin at Cycle 7 Day 28 will be created.

Mean and standard error will be plotted over time.

4.3.8.6. Platelet Count

Platelet counts will be summarized over time for all patients.

The number and percentage of patients with $\geq 30 \times 10^9/L$ increase in platelet count from baseline, the number and percentage of patients with $\geq 100\%$ increase in platelet count, and the number and percentage of patients with results within normal limits will be summarized at any time for CMML patients.

The maximum percent reduction from baseline and the maximum increase from baseline across all post-baseline visits will be summarized for CMML patients. A waterfall plot of the maximum increase in counts, counts at Cycle 4 Day 21 visit, and counts at Cycle 7 Day 28 will be created.

Mean and standard error will be plotted over time.

4.4. Safety Analyses

Safety analyses will be conducted using the Safety population and presented as described in [Section 3.5](#).

4.4.1. Study Drug Exposure

Duration of study drug exposure will be calculated as the number of days and number of cycles patients were administered study drug.

$$\text{Duration of Study Drug Exposure} = (\text{Date of last dose} - \text{Date of first dose}) + 1$$

Number of cycles of study drug initiated while the patient is on study will be summarized overall. Dose modifications, including the number of patients with dose interruptions or dose

reductions, will be summarized by cycle. Total dose administered will be summarized overall and number of doses administered will be summarized by cycle.

Relative Dose Intensity will be computed using the following definition and summarized by disease by trial stage:

$$\text{Relative Dose Intensity (\%)} = \frac{\text{Sum(Cumulative Actual Dose Received by Cycle)}}{\text{Sum(Planned Dose to be Administered by Cycle)}} \times 100$$

Exposure to tagraxofusp will be presented in a data listing based on Safety Population.

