8.2 Study Treatment Administration Schedule

Patients will receive 12 mcg/kg of tagraxofusp by IV infusion once daily for 3 consecutive days (or 3 doses over a period not to exceed 10 days if postponement is required to allow for toxicity resolution) of a cycle in the absence of PD or other withdrawal criteria.

A treatment cycle is 21 days in C1-4 and 28 days in C5 and beyond.

The total per-patient dose is calculated based on patient body weight in kg at baseline (C1D1). This dose will be recalculated if there is a 10% or greater change from baseline in body weight.

The first cycle of tagraxofusp must be administered in the inpatient setting, with hospitalization beginning the day of the first infusion of tagraxofusp (or a prior day) and ending approximately 24 hours after the last infusion of tagraxofusp. Subsequent cycles of tagraxofusp can be administered in the inpatient setting or in a suitable outpatient ambulatory care setting that is equipped for intensive monitoring of patients with hematopoietic malignancies undergoing treatment, per the Investigator's discretion, institutional guidelines, and capabilities. Patients will be monitored for at least 1 hour (or longer at the Investigator's discretion) following the administration of each infusion of tagraxofusp in Cycle 2 and beyond.

Patients with evidence of ongoing disease control during treatment (without evidence of clinically significant PD or intolerable toxicity) may receive repeated cycles of tagraxofusp even if an overall response, in the judgment of the Investigator, is not attained.

Refer to [Section 8.2.1](#) for details regarding required pre-medication, patient monitoring procedures, and dose modification procedures for the management of tagraxofusp-related toxicity.

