8.2.3.10.1 Nonhematological Toxicity

Table 1 summarizes the dose modification guidelines for tagraxofusp-related nonhematological toxicities (other than those identified in [Section 8.2.3.1](#) through [Section 8.2.3.8](#)).

Table 1: Dose Modifications for Other Tagraxofusp-Related Nonhematological Toxicity

CTCAE Grade	Tagraxofusp Dose Delays
Any Grade 1-2 toxicities	
 • No dose delay
Grade 3 with resolution to Grade \leq 1 or baseline by last day of cycle	
 • No dose delay
Grade 3 without resolution to Grade \leq 1 or baseline by last day of cycle	
 • Delay the start subsequent cycle by up to 14 days. – If after 14 days the toxicity resolves to Grade \leq 1 or baseline, no dose adjustment required and the cycle may start. – If after 14 days the toxicity has not resolved, monitor weekly until resolution; discuss additional dosing and schedule with the Medical Monitor.
Grade 4 (excluding transient [\leq 14 days] asymptomatic transaminase or CPK elevations) with resolution to Grade \leq 1 or baseline by last day of cycle	
 • The cycle may start.
Grade 4 without resolution to Grade \leq 1 or baseline by last day of cycle	
 • Delay the start subsequent cycle by up to 14 days. • If after 14 days the toxicity resolves to Grade \leq 1 or baseline, resume dosing.

CTCAE Grade	Tagraxofusp Dose Delays
	
 • If after 14 days the toxicity has not resolved, monitor weekly until resolution; discuss additional dosing and schedule with the Medical Monitor

Note that delays in start of subsequent cycles greater than 3 weeks will be acceptable only after discussion with the Medical Monitor regarding the potential risk/benefit of further treatment.

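### SAP 4.4.1 calls a ratio of actual to planned dose 'Relative Dose Intensity' although it has no time term; read over started cycles, it cannot show delayed cycles, and no other planned summary names them.

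*SAP*

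**What the plan says.** The exposure section of the SAP (4.4.1) announces the measure thus: "Relative Dose Intensity will be computed using the following definition and summarized by disease by trial stage". The numerator is "Sum(Cumulative Actual Dose Received by Cycle" and the denominator is "Sum(Planned Dose to be Administered by Cycle" (each with its closing bracket), times 100. The SAP does not say which cycles enter the denominator.

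The same section also plans:
- duration of exposure (last dose date minus first dose date, plus 1) and the number of cycles initiated;
- total dose, and number of doses by cycle;
- dose modifications by cycle, including interruptions and reductions;
- a listing of exposure.

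The Protocol gives the regimen in 8.2: "Patients will receive 12 mcg/kg of tagraxofusp by IV infusion once daily for 3 consecutive days", and "A treatment cycle is 21 days in C1-4 and 28 days in C5 and beyond".

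Protocol 8.2.3.10.1, Table 1, covers nonhematological toxicities other than those handled in 8.2.3.1 to 8.2.3.8. For Grade 3 or Grade 4 toxicity that has not resolved by the last day of the cycle, its action is "Delay the start subsequent cycle by up to 14 days". When Grade 3 toxicity then resolves, "no dose adjustment required and the cycle may start"; in the Grade 4 row dosing likewise resumes, and the table contains no dose-reduction level. A note adds that "delays in start of subsequent cycles greater than 3 weeks will be acceptable only after discussion with the Medical Monitor".

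**The concern.** Dose intensity means dose per unit time, and relative dose intensity compares the achieved rate with the planned rate. The SAP ratio compares amounts only. A patient who receives all three infusions in every cycle started scores 100% however far apart the cycles fall.

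The protocol foresees such delays. Besides Table 1, the guidance on hematological toxicity (8.2.3.10.2) allows therapy to be postponed in some patients, and the Stage 3A schedule (Table 4) has a column for an end of cycle delayed for toxicity resolution. Characterizing safety is the first-listed Stage 3A objective. A study report that gives a relative dose intensity near 100% invites the reader to conclude that the regimen was delivered on schedule, which this ratio cannot show.

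**Working it through.** The documents give no numerical relative dose intensity, so there is no planned figure to reproduce. The check applies the SAP formula and a time-based one to the same dosing histories.

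**Inputs**
- Planned dose per cycle: 3 × 12 = 36 mcg/kg (Protocol 8.2).
- Planned cycle length: 21 days in cycles 1 to 4, 28 days from cycle 5 (Protocol 8.2).
- Delay: up to 14 days before the next cycle, full dose afterwards (Protocol Table 1).
- Delay frequency: not documented, so a range is shown.

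**Formulas**
- SAP ratio = (sum of actual dose) / (sum of planned dose over started cycles) × 100.
- Time-based ratio = (actual dose / actual days) / (planned dose / planned days) × 100, where actual days run from first dose to the start of the last started cycle plus that cycle's planned length.
- When every dose is given, the time-based ratio reduces to planned days / (planned days + delay days) × 100.

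**All doses given**

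| History | SAP ratio | Time-based ratio |
|---|---|---|
| Four 21-day cycles, one 14-day delay | 144/144 = 100% | 84/98 = 85.7% |
| Same, two 14-day delays | 100% | 84/112 = 75.0% |
| Same, 7-day delays before cycles 2, 3 and 4 | 100% | 84/105 = 80.0% |
| Same, 14-day delays before cycles 2, 3 and 4 | 100% | 84/126 = 66.7% |
| Seven cycles (4 × 21 + 3 × 28 = 168 days), one 14-day delay | 100% | 168/182 = 92.3% |

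**Omitted doses.** With four cycles on time but two of three doses in each, both ratios are 96/144 = 66.7%. The SAP ratio registers omission; its blind spot is timing.

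**Which cycles count.** In the row with three 14-day delays, cycle 4 starts on day 106 and its third dose falls on day 108. Had the regimen run on time, cycles would have started on days 1, 22, 43, 64 and 85, so five were due by day 108. If the denominator counted cycles due by the last dose, the ratio would be 144/180 = 80%, not 100%. The wording 'by Cycle' points to started cycles, but the SAP does not say so.

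**The case against.** Several points on the other side are sound.

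**Omitted doses are captured, and they may matter more.** A reader might infer that the ratio misses the main form of under-dosing. The documents do not support that. Table 1 excludes the toxicities in 8.2.3.1 to 8.2.3.8. Protocol 4.4 lists transaminase elevations and manifestations of capillary leak syndrome among the most common events. Protocol 8.2.2, 8.2.3.3 and Appendix 18.3 manage these by withholding infusions within a cycle. Under 8.2.3, doses not given in the first 10 days are lost to that cycle. Every such loss lowers the SAP ratio.

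**The SAP does not call this its measure of tolerability.** A reader might assume that role from the name. In 4.4.1 it is one of several exposure summaries, with no stated purpose.

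**Delay is partly recoverable elsewhere.** With three 14-day delays, exposure duration over four cycles would be 108 days instead of 66, and cycles initiated are also reported. But duration is not combined with dose, and longer exposure can itself look favourable. The SAP's modification and adverse-event tables name interruptions and reductions, and the latter also discontinuations. Neither says whether a late cycle start counts as an interruption.

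**The 67% figure is extreme.** It needs the full 14-day delay before every cycle after the first, whereas Table 1 imposes none for Grade 1 or 2 toxicity or for Grade 3 toxicity that resolves in time. It should not be read as the expected intensity.

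**Little depends on it.** No hypothesis, endpoint or decision rule uses the measure, and SAP Section 5 says that enrollment into Stage 3A was not continued and that the analyses will be descriptive.

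Together these points limit the size and reach of the problem. They leave untouched that the label promises a rate, the formula gives an amount, and no planned table names cycle delays.

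**Conclusion.** The point holds as a mislabelled measure with a specific blind spot. Following the SAP exactly on the started-cycles reading would report 100% for a fully dosed patient whose cycles are late, and the difference from the time-based figure always flatters delivery on schedule. One 14-day delay in four to seven cycles puts the time-based figure at about 86% to 92%; maximum delays before each of cycles 2 to 4 put it at 67%.

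This rests on two assumptions: that the denominator sums over started cycles, which is the natural but unstated reading, and that all doses are given in the illustrations. How often delays occurred cannot be judged from the documents. The change is worth making before the study report is written, but no conclusion about efficacy depends on it.

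**What to change.** 1. Rename the present ratio 'percentage of planned dose received' and state that both sums run over started cycles.
2. Add relative dose intensity = (actual cumulative dose / actual time) / (planned dose / planned time) × 100, with actual time from first dose to the start of the last started cycle plus that cycle's planned length. This end point also settles how to treat patients who stop mid-cycle.
3. Tabulate the number and duration of cycle delays by disease and trial stage, with the reason where it is recorded, since a postponement under 8.2.3.10.2 may not mean poor tolerability.
4. Define planned time by stage. This first requires reconciling the Stage 2 schedule: SAP 1.1.2 puts Stage 2 on the Stage 1 schedule, with 42-day cycles from cycle 8, while SAP 1.2.1.2 gives 28 days from cycle 5 onward. Protocol Section 1 also puts Stage 3A on the Stage 1 schedule, against the 28 days from cycle 5 in Protocol 8.2, so that statement needs reconciling too.

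The cost is one derived variable and one table, from dosing dates that the duration formula already uses, plus the effort of settling the schedules. Reported intensity may come out less favourable.
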